### 9.9.2 Secondary Efficacy Endpoints

The secondary efficacy endpoints include the following variables:

- Clinical outcome per patient at EOT and FUP (HAP/VAP/HCAP or BSI/sepsis)
- Clinical outcome per pathogen at EOT, TOC, and FUP (HAP/VAP/HCAP or BSI/sepsis)
- Clinical outcome per patient/pathogen at EOT, TOC, and FUP (cUTI)
- Microbiologic outcome (for Gram-negative pathogen) per patient/pathogen at EOT, TOC, and FUP (HAP/VAP/HCAP or BSI/sepsis)
- Microbiologic outcome (for Gram-negative pathogen) per patient at EOT, and FUP (cUTI)
- Microbiologic outcome (for Gram-negative pathogen) per pathogen at EOT, TOC, and FUP (cUTI)
- Microbiologic outcome with documented carbapenem-resistant Gram-negative bacteremia (regardless of primary infection diagnosis) at EOT, TOC, and FUP
- Composite clinical and microbiologic outcome at EOT, TOC, and FUP
- All-cause mortality at Day 14 and Day 28 for HAP/VAP/HCAP and BSI/sepsis
- Composite endpoint of survival and no change in antibiotic treatment due to either lack of therapeutic benefit or drug-related toxicity at TOC
- Survival time (HAP/VAP/HCAP, BSI/sepsis)
- CPIS parameters at EOT and TOC (HAP/VAP/HCAP only)
- SOFA Score at EOT, and TOC

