### 3.2 Secondary Objectives

- To assess the safety of cefiderocol
- To assess the clinical outcome of treatment with cefiderocol or BAT in subjects with either HAP/VABP/HCABP or BSI/sepsis at End of Treatment (EOT) and Follow-up (FU)
- To assess the clinical outcome of treatment with cefiderocol or BAT in subjects with cUTI at EOT, TOC, and FU

- To assess the microbiological outcome of treatment with cefiderocol or BAT in subjects with either HABP/VABP/HCABP or BSI/sepsis at EOT, TOC, and FU
- To assess the microbiological outcome of treatment with cefiderocol or BAT in subjects with cUTI at EOT and FU
- To assess the microbiological outcome of treatment with cefiderocol or BAT in subjects with bacteremia (regardless of the primary infection diagnosis) at EOT, TOC, and FU
- To assess the composite clinical and microbiological outcome of treatment with cefiderocol or BAT in subjects with cUTI at EOT, TOC, and FU
- To assess the all-cause mortality at Day 14 and Day 28 in subjects with HABP/VABP/HCABP and BSI/sepsis
- To compare cefiderocol with BAT in subjects with HABP/VABP/HCABP, cUTI, or BSI/sepsis based on the composite endpoint of survival and no change in antibiotic treatment due to either lack of therapeutic benefit or drug-related toxicity at TOC

 TOC is defined as End of Treatment (EOT) + 7 days ( $\pm$  2 days).

 BSI/sepsis is a group of patients with documented carbapenem-resistant Gram-negative infections in the bloodstream (BSI) or in a body site other than the urinary tract (cUTI) or lung (HABP/VABP/HCABP) and in case of sepsis, evidence of systemic inflammatory response syndrome (SIRS) is required.

 EOT = End of Treatment is defined as the last day of study therapy.

 FU = Follow-up is defined as EOT + 14 days ( $\pm$  3 days).

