### 9.3.3 Subgroup Analyses

Clinical outcome and microbiological outcome per subject at TOC will be summarized by age group, gender, race, and infection site, type of baseline CR pathogen, APACHE II score ( $\leq 15$  and  $\geq 16$ ), and region (North America, South America, Europe, and Asia-Pacific) for the CR Micro-ITT population. The same analysis will be applied for microbiological outcome, and 28 days all-cause mortality.

Other subgroup analyses may be performed if deemed necessary.

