## 9.4 Secondary Endpoints

The secondary endpoints of this study are the following:

- Clinical outcome per subject at EOT and FU (HABP/VABP/HCABP or BSI/sepsis)
- Clinical outcome per pathogen at EOT, TOC, and FU (HABP/VABP/HCABP, BSI/sepsis or cUTI)
- Clinical outcome per subject/pathogen at EOT, TOC, and FU (cUTI)
- Clinical outcome per subject/pathogen at EOT, TOC, and FU (HABP/VABP/HCABP + BSI/sepsis, overall)
- Clinical outcome per CR pathogen at EOT, TOC, and FU (HABP/VABP/HCABP, BSI/sepsis, cUTI, HABP/VABP/HCABP + BSI/sepsis, overall)
- Microbiological outcome (for baseline Gram-negative pathogens) per subject/pathogen at EOT, TOC, and FU (HABP/VABP/HCABP or BSI/sepsis)
- Microbiological outcome (for baseline Gram-negative pathogens) per subject at EOT and FU (cUTI)
- Microbiological outcome (for baseline Gram-negative pathogens) per pathogen at EOT, TOC, and FU (cUTI)
- Microbiological outcome (for baseline Gram-negative pathogens) per subject/pathogen at EOT, TOC, and FU (HABP/VABP/HCABP + BSI/sepsis, overall)

- Microbiological outcome (for baseline CR Gram-negative pathogens) per subject at EOT, TOC and FU (HABP/VABP/HCABP, BSI/sepsis, cUTI, HABP/VABP/HCABP + BSI/sepsis, overall)
- Microbiological outcome (for baseline CR Gram-negative pathogens) per pathogen at EOT, TOC, and FU (HABP/VABP/HCABP, BSI/sepsis, cUTI, HABP/VABP/HCABP + BSI/sepsis, overall)
- Microbiological outcome with documented carbapenem-resistant Gram-negative bacteremia (overall) at EOT, TOC, and FU
- Composite clinical and microbiological outcome at EOT, TOC, and FU (HABP/VABP/HCABP, BSI/sepsis, cUTI)
- All-cause mortality at Day 14 and Day 28
- Composite endpoint of survival and no change in antibiotic treatment due to either lack of therapeutic benefit or drug-related toxicity at TOC
- Survival time (HABP/VABP/HCABP, BSI/sepsis)
- CPIS parameters at EOT, TOC, and FU (HABP/VABP/HCABP only)
- SOFA score at EOT, TOC, and FU

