#### **9.4.1.6 All-cause Mortality and Survival Time**

All-cause mortality rate with 95% CI at Day 14, Day 28 and overall by treatment group will be calculated as the proportion of subjects who experienced mortality regardless of the cause at or before Day 14 and Day 28, respectively. In this analysis, deaths occurring after EOS will not be used for analysis and any subject who does not have vital status information at Day 14 and 28 will not be included in the analysis. This analysis will be performed for both CR MITT and ITT Population.

In addition, for CR MITT Population, subgroup analysis regarding all-cause mortality at Day 28 will be performed. For the survival time up to End of Study (EOS), the survival curve using Kaplan-Meier method by treatment group will be presented. For the subjects whose vital status is survival at EOS, the subjects will be treated as right-censored at EOS. For the subjects whose vital status is not collected or unknown, the subjects will be treated as right-censored at last visit day.

All-cause mortality rate at Day 14, Day 28 and overall including death after EOS will be calculated by treatment group for ITT population.

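### SAP 9.4.1.6 specifies Day 14 and Day 28 mortality without the pneumonia and BSI/sepsis restriction that the protocol and SAP 3.2 put on that endpoint

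*SAP*

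**What the plan says.** Protocol 2.2 limits the mortality objective to pneumonia and BSI/sepsis, and Protocol 9.9.2 lists the endpoint as "All-cause mortality at Day 14 and Day 28 for HAP/VAP/HCAP and BSI/sepsis". Survival time carries the same limit in that list: "Survival time (HAP/VAP/HCAP, BSI/sepsis". SAP 3.2 keeps the mortality objective unchanged: "To assess the all-cause mortality at Day 14 and Day 28 in subjects with HABP/VABP/HCABP and BSI/sepsis".

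The SAP 9.4 endpoint list then gives Day 14 and Day 28 mortality with no site named, although its survival line still reads "Survival time (HABP/VABP/HCABP, BSI/sepsis".

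SAP 9.4.1.6 is the analysis paragraph. It states that "All-cause mortality rate with 95% CI at Day 14, Day 28 and overall by treatment group will be calculated", and "This analysis will be performed for both CR MITT and ITT Population". For time to death, "the survival curve using Kaplan-Meier method by treatment group will be presented". It mentions no infection site.

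Two other places bear on the point. SAP 9.3.3 has infection site among its subgroup variables in CR Micro-ITT and extends those subgroups to microbiological outcome "and 28 days all-cause mortality". SAP 15 declares, as changes from the protocol, a cUTI mortality analysis, a mortality subgroup analysis, and a general pneumonia plus BSI/sepsis grouping for efficacy endpoints.

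**The concern.** The objective, the endpoint line and the analysis paragraph do not agree on whose mortality is measured. Someone programming from 9.4.1.6 would produce rates over all three infection sites, and those rates answer a different question from the stated objective.

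The difference matters because the sites are not interchangeable. Protocol 3.2.1 describes bacteremia, septicemia and lung infection as harder to treat than urinary infection and caps cUTI for that reason. Adding lower-risk patients lowers the rate in each arm. If treatment makes no difference to mortality in cUTI, it also shrinks any difference between arms, whether that difference favours the drug or is adverse. With no formal test of mortality, the reported rates and intervals are the whole result, so the population behind them should be the one in the objective.

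**Working it through.** **Step 1. The plan's own figure.** About 150 patients randomized 2:1 (Protocol 9.2, SAP 4.3) gives 150 × 2/3 = 100 and 150 × 1/3 = 50, which matches the stated 100 or so treated with the study drug. The documents give no mortality rate, event count or power to reproduce.

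**Step 2. What is specified for the protocol's group.**

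| Result | All sites | By site | Pneumonia + BSI/sepsis combined |
|---|---|---|---|
| Day 14, CR Micro-ITT | 9.4.1.6 | not specified | not specified |
| Day 28, CR Micro-ITT | 9.4.1.6 | 9.3.3 | only by adding the two site counts; no combined rate or CI |
| Day 14 and Day 28, ITT | 9.4.1.6 | not specified | not specified |
| Survival curve | 9.4.1.6 names no site | not specified | 9.4 restricts the endpoint; 9.4.1.6 does not repeat it |

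Neighbouring sections are explicit. SAP 9.4.1.1 to 9.4.1.4 name the pneumonia plus BSI/sepsis group and the overall group. SAP 9.4.1.5, 9.4.1.7 and 9.4.1.9 ask for results by infection site.

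**Step 3. Size of the set.** The cUTI share s is at most 0.30 (Protocol 4.1, SAP 4.2). At the cap, the protocol's group is 150 × 0.70 = 105 patients (70 vs 35). At s = 0.20 it is 120 (80 vs 40).

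**Step 4. Effect of an all-site rate.** Let p be an arm's mortality in pneumonia plus BSI/sepsis and u the cUTI mortality, equal in both arms.

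All-site rate = (1 − s) × p + s × u

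All-site difference = (1 − s) × (p₁ − p₂), because the u terms cancel.

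The multiplier is 0.70 at the cap and 0.80 at s = 0.20.

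**Step 5. Illustration at the cap, with assumed rates.** Take 30% on cefiderocol, 20% on BAT, and u from 0% to 15%.

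- Cefiderocol all-site: 0.7 × 30 + 0.3 × u = 21.0% to 25.5%.
- BAT all-site: 0.7 × 20 + 0.3 × u = 14.0% to 18.5%.
- Difference: 0.7 × 10 = 7.0 points instead of 10. At s = 0.20 it is 8.0. Swapping the arms gives the same shrinkage.
- Wald 95% half-width, restricted set: 1.96 × √(0.20 × 0.80/35 + 0.30 × 0.70/70) = 17.1 points.
- The same formula with 50 and 100 patients and the all-site rates: 12.5 points (u = 0%) to 13.7 points (u = 15%).
- Difference divided by its standard error: 1.15 restricted, 1.10 to 1.00 all-site, a loss of about 4% to 13%.

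For a single arm with the Clopper-Pearson interval that SAP 9 prescribes, 21 deaths in 70 patients is 30% (19.6% to 42.1%). Adding 30 cUTI patients with 2 deaths gives 23 in 100, or 23% (15.2% to 32.5%).

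**The case against.** The strongest reply is that little is lost. SAP 9.4.1 introduces its analyses as those of the endpoints listed in 9.4, and 9.4 keeps the site limit for survival time, so the Kaplan-Meier curve can be read as inheriting it. Day 28 mortality by site is planned in CR Micro-ITT, and the pneumonia and BSI/sepsis counts can be added. The cUTI mortality analysis is openly declared in SAP 15, which also adds a general pneumonia plus BSI/sepsis grouping for efficacy endpoints. Table layouts sit in a separate document that is not available here. All-site mortality also has a legitimate place, since Protocol 9.10 counts mortality among the safety assessments.

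Most of this stands, and it rules out several stronger inferences.

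- A reader might infer that survival curves are to be pooled over sites. SAP 9.4 says otherwise; 9.4.1.6 is silent rather than contradictory.
- A reader might infer that the protocol endpoint is never produced. For Day 28 in CR Micro-ITT it can be rebuilt, and the general bullet in SAP 15 may be meant to cover mortality.
- A reader might call this a key secondary result whose test is weakened. Neither document ranks the secondary endpoints. SAP 6.2 rules out inferential testing apart from one exploratory analysis, which is not mortality. SAP 9.4.1.6 plans rates per arm, not a tested difference.
- A reader might expect unequal cUTI shares to confound the comparison. With 30% and 5% mortality in both arms, shares of 20% and 30% would give 25.0% against 22.5%, a spurious 2.5 points. But infection site is a minimization factor. CR Micro-ITT is selected after randomization, so balance there is not guaranteed, yet nothing supports an imbalance of that size.

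The reply does not supply the missing text. Declaring an added cUTI analysis does not say that the protocol's population has been replaced, and the general bullet in SAP 15 is not carried into 9.4.1.6.

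**Conclusion.** The concern holds as an inconsistency in which patients the mortality analysis covers. SAP 3.2 and the protocol restrict Day 14 and Day 28 mortality to pneumonia and BSI/sepsis; SAP 9.4 and 9.4.1.6 do not. Day 14 mortality and all ITT mortality for the protocol's group are unspecified, Day 28 in CR Micro-ITT lacks a combined rate and interval, and 9.4.1.6 leaves the site limit on survival time unstated.

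If the all-site rate is reported as the result, the arm difference is multiplied by one minus the cUTI share, so it is reduced by up to 30% at the cap. That rests on equal cUTI mortality in the two arms and on a cUTI share in the analysed set no larger than the randomization cap. The point figures in the illustration depend on assumed rates. The larger all-site sample offsets most of the loss in precision terms, so the harm is to what the estimate means rather than to power or an error rate.

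**What to change.** In SAP 9.4.1.6, name HABP/VABP/HCABP + BSI/sepsis as the protocol-defined set for Day 14 mortality, Day 28 mortality and the Kaplan-Meier curve, with the mortality rates and 95% CIs given in both CR Micro-ITT and ITT. Report each infection site, including cUTI, and the all-site total as added analyses. Restore the site restriction in the mortality line of SAP 9.4, and adjust SAP 15 so that 3.2, 9.4, 9.4.1.6 and 15 describe the same populations.

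The cost is SAP wording and one population flag in existing tables. The named set has up to about 30% fewer patients (105 rather than 150 at the cap, before any CR Micro-ITT exclusions) and correspondingly wider intervals. The all-site table is kept, so no planned result is lost.

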#### **9.9.4 Secondary Efficacy Analyses**

The secondary endpoint of clinical response rates and microbiological response rates by treatment group and the 95% CIs will be calculated.

Composite clinical and microbiologic response rates by treatment group and the 95% CIs will be calculated.

Survival analysis of all-cause mortality will be performed.

The response rate of a composite endpoint of survival and no change in antibiotic treatment due to either lack of therapeutic benefit or drug-related will be compared between treatment groups by infection site (HAP/VAP/HCAP, cUTI, or BSI/sepsis) at TOC.

SOFA and CPIS (ventilated only) scores by infection site as relevant will be summarized by timepoint.

Descriptive statistics for all efficacy parameters will be provided.

Details for the secondary efficacy analyses will be discussed in the SAP.

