### 6.2 Statistical Testing

No inferential testing will be performed except for the exploratory analysis described in Section 9.4.1.7. If statistical tests are performed, they will be performed at the 0.05 significance level using 2-sided tests, except where otherwise noted. No multiplicity adjustment of statistical tests will be applied in this study.

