### **9.3.1 Primary Analyses for the Primary Efficacy Endpoint**

For the CR Micro-ITT population, the following analysis will be performed.

The clinical outcomes at TOC will be summarized and clinical cure rates and its 95% CIs will be calculated by treatment group (cefiderocol or BAT) for subjects with HABP/VABP/HCABP or BSI/sepsis, separately. The clinical response rate will be calculated as the proportion of subjects whose clinical outcome is clinical cure at TOC.

The microbiological outcomes at TOC will be summarized and microbiological eradication rates and its 95% CIs will be calculated by treatment group (cefiderocol or BAT) for the subjects with cUTI. The microbiological response rate will be calculated as the proportion of subjects whose all of baseline Gram-negative uropathogen(s) are eradicated at TOC.

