#### **9.4.1.9 Composite of Survival and No Change in Antibiotic Treatment**

For the composite of survival and no change in antibiotic treatment due to either lack of therapeutic benefit or drug-related toxicity at TOC, the response rate with 95% CI by treatment group per infection site will be presented. This composite endpoint will be assessed by Shionogi medical expertise internally. The response rate in the cefiderocol treatment group will be compared with that in the BAT group using Cochran Mantel-Haenszel Method stratified by infection site. The 95% CI will be calculated by Wald method (see [Appendix 2](#)).

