## Appendix 2 Calculation Confidence Interval for Cochran-Mantel-Haenzel Test

Let  $x_{ij}$  and  $n_{ij}$  denote the number of responders and the total number of patients in treatment  $i$  and stratum  $j$ , respectively, where  $i=1,2$  represents the treatment group (cefiderocol or BAT) and  $j = 1,2,3$  represents the stratum, the following  $2 \times 2$  contingency table shows the total number of subjects and the number of responders in each treatment arm at stratum  $j$ .

Category	cefiderocol	BAT
Response	$x_{1j}$	$x_{2j}$
No Response	$n_{1j} - x_{1j}$	$n_{2j} - x_{2j}$
Total	$n_{1j}$	$n_{2j}$

The proportion of patients with response ( $\pi_{ij}$ ) in treatment  $i$  and stratum  $j$  can be estimated by:

$$\hat{\pi}_{ij} = x_{ij}/n_{ij}$$

and the stratum-specific proportion difference ( $d_j$ ) is estimated by:

$$\hat{d}_j = \hat{\pi}_{1j} - \hat{\pi}_{2j}.$$

The adjusted estimate of the difference in the rate of responders between the two treatment groups ( $d_{adj}$ ) is given as:

$$\hat{d}_{adj} = \sum_{j=1}^3 w_j \hat{d}_j$$

using the CMH weights defined as  $w_j = \left( \frac{n_{1j}n_{2j}}{n_{1j}+n_{2j}} \right) / \sum_{j=1}^3 \frac{n_{1j}n_{2j}}{n_{1j}+n_{2j}}$ .

Hence, the 2-sided stratified 95% Wald-type confidence intervals of  $d_{adj}$  based on the CMH weights is constructed as:

$$\hat{d}_{adj} \pm z_{\alpha/2} \text{Var}(\hat{d}_{adj}),$$

where the variance of  $d_{adj}$  is given as:

$$\text{Var}(\hat{d}_{adj}) = \sqrt{\sum_{j=1}^3 \hat{w}_j^2 \left( \frac{\hat{\pi}_{1j}(1 - \hat{\pi}_{1j})}{n_{1j}} + \frac{\hat{\pi}_{2j}(1 - \hat{\pi}_{2j})}{n_{2j}} \right)},$$

and  $z_{\alpha/2}$  is the 97.5th percentile of the standard normal distribution.

[REDACTED] [REDACTED]  
Reason for signing: Approved

[REDACTED]  
Date of signature: 27-Jun-2019 17:37:01 GMT+0000

Reason for signing: Approved

[REDACTED]  
Date of signature: 27-Jun-2019 18:12:40 GMT+0000

Signature Page for [REDACTED]

[REDACTED]

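### Mortality and the primary outcomes get per-arm rates but no between-arm difference with a confidence interval, and the mortality rates drop patients whom the Kaplan-Meier curve keeps

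*SAP*

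**What the plan says.** **Mortality.** SAP 9.4.1.6 plans "All-cause mortality rate with 95% CI at Day 14, Day 28 and overall by treatment group", in the CR Micro-ITT and ITT populations, with Kaplan-Meier curves by arm up to EOS. It names no difference, ratio or test. Protocol 9.9.4 says "Survival analysis of all-cause mortality will be performed" and leaves the detail to the SAP, which adds only the curves.

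**Unknown vital status.** Two rules stand in the same section. For the rates, "any subject who does not have vital status information at Day 14 and 28 will not be included in the analysis". For the curve, "For the subjects whose vital status is not collected or unknown, the subjects will be treated as right-censored at last visit day".

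**Primary outcomes.** SAP 9.3.1: "The clinical outcomes at TOC will be summarized and clinical cure rates and its 95% CIs will be calculated by treatment group", by infection site. Eradication in cUTI is handled in the same way. SAP 9 makes the single-proportion Clopper-Pearson interval the default.

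**The one contrast.** SAP 9.4.1.9 covers the composite of survival and no change in antibiotic treatment, which the sponsor assesses internally: "The response rate in the cefiderocol treatment group will be compared with that in the BAT group". Appendix 2 supplies "The adjusted estimate of the difference in the rate of responders between the two treatment groups" and its interval.

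**Testing.** SAP 6.2: "No inferential testing will be performed except for the exploratory analysis described in Section 9.4.1.7". Section 9.4.1.7 is the SOFA summary, which contains no test. The comparison is in 9.4.1.9.

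**The concern.** The trial is open-label, and the clinical outcome is judged by investigators who know the treatment. Death is the efficacy endpoint least open to that bias. Yet the plan gives no measure of uncertainty for the randomised comparison of deaths, and gives one for a composite judged by the sponsor.

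Two per-arm intervals do not fill the gap. They can overlap when the interval for the difference excludes zero, so a reader who compares them by eye may miss either harm or benefit.

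Three smaller points sit in the same sections.

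- The mortality table and the mortality curve use different patients. The exclusion rule also does not say whether a patient missing only one of the two days leaves both rates.
- Overall mortality is a raw proportion up to EOS. EOS is tied to the end of treatment, so patients are followed for different lengths of time.
- Read literally, SAP 6.2 excludes the only comparison that the SAP plans.

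**Working it through.** **Inputs from the documents.** About 150 patients are randomised 2:1 (SAP 4.3). 150 × 2/3 = 100 on cefiderocol, which reproduces the stated figure, and 150 × 1/3 = 50 on BAT. Site shares are about 50% pneumonia, at most 30% cUTI and the rest BSI/sepsis (SAP 4.2), which gives 50 v 25, 30 v 15 and 20 v 10. EOS is EOT + 28 days.

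**Assumptions.** The documents give no mortality, response or unknown-status rate. I take BAT mortality of 10% to 30%, response of 60% in both arms, and 2% or 8% of unknown status per arm.

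**1. Per-arm intervals against an interval for the difference.** The Newcombe limits for d = p1 − p2, with Wilson limits (l, u) for each arm, are

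- lower = d − √[(p1 − l1)² + (u2 − p2)²]
- upper = d + √[(u1 − p1)² + (p2 − l2)²]

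Take 36/100 v 10/50. The Wilson limits are 27.3–45.8% and 11.2–33.0%, and d = 16.0 points.

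- lower = 16.0 − √(8.7² + 13.0²) = 0.3
- upper = 16.0 + √(9.8² + 8.8²) = 29.1

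The SAP's Clopper-Pearson intervals for the same data are 26.6–46.2% and 10.0–33.7%, which overlap. They first separate at 44 cefiderocol deaths, where the lower limit is 34.1%.

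The same search over other BAT counts, with cefiderocol deaths per 100:

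| BAT deaths of 50 | Difference CI excludes 0 (harm) | Fisher two-sided p < 0.05 (harm) | Per-arm CIs separate (harm) | Difference CI excludes 0 (benefit) | Per-arm CIs separate (benefit) |
|---|---|---|---|---|---|
| 5 | 24 | 24 | 31 | ≤ 2 | never |
| 8 | 31 | 32 | 39 | ≤ 5 | ≤ 2 |
| 10 | 36 | 37 | 44 | ≤ 8 | ≤ 4 |
| 12 | 41 | 41 | 49 | ≤ 11 | ≤ 6 |
| 15 | 47 | 48 | 55 | ≤ 16 | ≤ 10 |

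Fisher's test stays within one death of Newcombe, so the gap does not come from the choice of interval.

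**2. Unknown vital status.** Assume 25/100 v 10/50 known deaths. The bounds on the difference count the unknowns as dead in one arm and alive in the other.

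- 2% unknown per arm: exclusion gives 25/98 − 10/49 = 5.1 points. Bounds: 25/100 − 11/50 = 3.0 and 27/100 − 10/50 = 7.0.
- 8% unknown per arm: exclusion gives 25/92 − 10/46 = 5.4 points. Bounds: 25/100 − 14/50 = −3.0 and 33/100 − 10/50 = 13.0.

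The two rules also disagree on the same data. Take 50 patients with 10 deaths and 5 unknown. Exclusion gives 10/45 = 22.2%. Kaplan-Meier gives 10/50 = 20.0% if all deaths come before the censoring. It gives 1 − (45/50)(35/40) = 21.3% if 5 deaths come before and 5 after.

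**3. Follow-up behind overall mortality.** EOS day = treatment days + 28. Seven days of treatment gives Day 35 and 21 days gives Day 49, which matches the 5 to 7 weeks in protocol 3.3.1. The ±3-day visit window widens this. Protocol Appendix 1 allows EOT at any time after the first dose, and EOT on Day 3 would put EOS at Day 31.

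**4. Which interval.** Coverage was found by exact enumeration, for BAT mortality of 10–30% at 100 v 50 and response of 40–70% at the three site sizes.

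| Interval | 100 v 50 | Site sizes |
|---|---|---|
| Newcombe | 94.8–95.8% | 94.0–95.4% |
| Unstratified Wald | 93.9–94.4% | 91.5–93.9% |

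With no censoring, the Wald interval equals the Kaplan-Meier difference with Greenwood variance. That is adequate for mortality at 100 v 50. At the site sizes Newcombe is the better choice.

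**The case against.** The plan is descriptive by declaration. The objectives speak of assessing the primary outcomes and mortality, and of comparing only for the composite. Protocol 9.9.3 promises per-arm rates, and the sample size rests on feasibility and discussion with the EMA, with no power or margin. The SAP therefore does what the protocol announced. That stands, and it is why this is a weak choice and not an inconsistency. It does not remove the case for a difference with an interval, which is an estimate and needs neither a test nor an alpha.

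A reader with both counts can compute the interval. That is true of a simple proportion. But the method would then be picked after the results are known, and counts alone do not give a Kaplan-Meier contrast when patients are censored. The separation of per-arm intervals is not a criterion in the SAP either; the table shows only what reading them side by side can hide.

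Few patients may be of unknown status. The protocol records dates of death, allows EOS by telephone and follows patients who stop treatment. At 2% unknown the effect is indeed small. Kaplan-Meier also assumes non-informative censoring, so the bounds are needed beside it.

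The site-level widths quoted under the fix are a best case, because the primary population is CR Micro-ITT and not all randomised patients. If 20% were lost, BSI/sepsis at 16 v 8 would run from about −34 to 37 points. Infection site is also an allocation factor, so a site-stratified mortality difference would be a reasonable addition. Finally, overall mortality matters less than the rest, because the fixed-day rates and the curve are already planned, and the SAP adds ITT rates that include deaths after EOS. These points refine the proposal and leave it standing.

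**Conclusion.** The concern holds, and the change should be made. The SAP gives no interval for the between-arm difference in mortality or in any primary outcome, and it treats unknown vital status in two ways within one section. At 100 v 50 and assumed BAT mortality of 10% to 30%, 7 or 8 more cefiderocol deaths per 100 are needed before the per-arm intervals separate than before the interval for the difference excludes zero. The effect of the exclusion rule depends on how many patients are lost and what happened to them: bounds of 3.0 to 7.0 points at 2% unknown, and −3.0 to 13.0 at 8%. All event and loss rates here are assumptions. The wrong section number in SAP 6.2 is a plain error, and overall mortality is a lesser point.

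**What to change.** In SAP 9.4.1.6:

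- Estimate Day 14 and Day 28 mortality by Kaplan-Meier in all ITT and all CR Micro-ITT patients, with unknowns censored at last contact.
- Add best-case and worst-case bounds for the unknowns.
- Add the cefiderocol minus BAT difference with 95% CI at each day, labelled descriptive.
- Report overall mortality as a Kaplan-Meier estimate at one fixed day.

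In SAP 9.3.1, add the difference with a Newcombe 95% CI for each primary outcome within its infection site, labelled descriptive. Keep the site-stratified comparison of the composite as planned. In SAP 6.2, change the reference from 9.4.1.7 to 9.4.1.9.

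The cost is SAP wording and a few table rows, with no new data. The downside is wide intervals. At 60% response in both arms and the planned site shares, they run from −21.6 to 22.9 points for pneumonia (50 v 25), −26.8 to 28.7 for cUTI (30 v 15) and −31.5 to 34.0 for BSI/sepsis (20 v 10). They show how little 150 patients can exclude, which side-by-side rates leave unsaid.
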